1 ABSTRACT

A novel type of non-cigarette tobacco product was recently approved for sale in the US, the heated tobacco product (HTP) IQOS. IQOS may be less harmful than cigarettes, and there are some reports that it may produce more rewarding subjective effects compared to e-cigarettes. The approval of IQOS provides a unique opportunity to gather preliminary data surrounding IQOS. The goal of this pilot study is to assess the subjective effects and relative reinforcement value of IQOS, including its downstream effects on cigarette smoking. Current smokers will complete a one-week baseline period where they smoke as normal before attending an in-person lab visit. During the in-person lab visit, participants (n=10) will sample a traditional cigarette and a novel IQOS tobacco product. Participants will answer questionnaires about each product they sample and then complete a preference assessment in which they choose between the IQOS and their own cigarette. Finally, participants will take home a tobacco product they sampled to use ad libitum (1-week sampling). During the at-home baseline and sampling weeks, participants will complete electronic daily diaries cataloging their tobacco use. Biomarkers (i.e., expired carbon monoxide, cotinine) will corroborate self-reported indices of use.

2 OBJECTIVES

2.1 OBJECTIVES

To directly compare a novel tobacco product (IQOS) vs. combustible cigarettes on subjective effects and reinforcement value as well as test the impact of IQOS on tobacco use patterns (i.e., cigarettes per day) among current smokers.

Hypothesis: Given that there are no existing data comparing IQOS to traditional cigarettes, we make no *a priori* hypothesis about which product will have greater subjective effects or reinforcement value. We make no *a priori* hypothesis about the impact of IQOS on tobacco use.

3 BACKGROUND AND SIGNIFICANCE

In April of 2019, the FDA approved the sale of IQOS, a novel HTP that has been available for some time in other countries. IQOS heats disposable tobacco sticks (Heat Sticks) which are inserted into a holder and heated with an electric blade at 350°C[1]. IQOS is currently available in Japan, Italy, Switzerland, South Korea, and has been increasing in prevalence in these countries. IQOS is being marketed as an alternative to smoking for current smokers. Existing data suggest that it likely does provide reduced toxicant exposure compared to smoking for current smokers, although the levels of toxicant exposure may be greater for IQOS than they are for e-cigarettes [2]. If IQOS proves to be a more appealing product than e-cigarettes and produces greater uptake and greater downstream effects on cigarette

smoking, IQOS could have a more positive impact on public health than e-cigarettes, despite the direct health effects of IQOS likely being more harmful than e-cigarettes. However, because IQOS was only recently approved for sale in the US, there is no existing US research on its appeal or reinforcement value.

The proposed pilot is innovative in that it will be the first study to provide the IQOS product to US smokers outside of the tobacco industry and will provide important preliminary data for a future grant application focused on IQOS.

3.1 INTERVENTION TO BE STUDIED (USE OF HTP)

Heated Tobacco Products (HTPs, sometimes called Heat Not Burn or HNB) are quite different from both e-cigarettes and traditional cigarettes. HTPs heat reconstituted tobacco at a temperature below combustion of the tobacco rod as is the case for a conventional cigarette. Because the tobacco is not directly burned, exposure to the many harmful chemicals generated by cigarette smoke is substantially lower for HTPs [3]. Because actual tobacco is used (vs glycerin liquid within e-cigarettes), HTPs products may provide a superior sensory experience to e-cigarettes [3]. However, the tobacco is singed within HTPs, and thus these products most likely result in increased exposure to harmful chemicals compared to e-cigarettes, though still less than combustibles.

Tobacco Products are regulated by the FDA. An Investigational Tobacco Product (ITP) application to the FDA is not required because both products are approved for commercial sale in the US. An Investigational New Drug (IND) application would be required if we were testing the impact of IQOS on smoking cessation but is not required in this case because we are interested in the naturalistic impact of these products on tobacco use generally. We have conducted multiple studies of this type and have strong confidence that we are on safe regulatory ground in conducting the study without an ITP/IND.

[name] has three recently completed or ongoing trials investigating the impact of providing other non-cigarette products to smokers on tobacco use patterns. These trials are very similar to the proposed project in that smokers are recruited to receive an e-cigarette, which is provided in a naturalistic way to be used as much or as little as the smoker wishes. While [name] has not led trials of IQOS, neither has any other US investigator.

4 ELIGIBILITY CRITERIA

4.1 INCLUSION CRITERIA

To be eligible for this study, the participant must meet all of the following criteria:

1. have been smoking at least five cigarettes daily for the past year (baseline carbon monoxide > 8ppm)
2. rate their interest in using non-cigarette tobacco products as >5 on a 0-10 scale

3. have a smartphone that can receive text messages and has access to the internet or have an e-mail account they check daily (necessary for daily diary completion).

4.2 EXCLUSION CRITERIA

To be eligible for this study, the participant CANNOT meet any of the following criteria:

1. purchasing a heated tobacco product within the last six months
2. weekly use of heated tobacco product over the last six months
3. any heated tobacco product use in the past 30 days
4. use of tobacco products other than cigarettes on ten or more days in the past 30 days
5. current use of cessation medications
6. pregnant, trying to become pregnant, or breastfeeding
7. recent history of cardiovascular distress in the last three months
8. history of a seizure disorder
9. household member currently enrolled.

5 PROCEDURES

Design Overview: After completing a screening/baseline session, current smokers will complete a one-week baseline period. Participants will then attend a lab-reinforcement session where they will sample the IQOS product and a traditional cigarette. We will provide transportation via a taxi cab company (Yellow Cab) for participants who are eligible, but do not have reliable transportation to in-person visits. We will pay the cab company directly, the participant will not need to contribute. Participants will complete questionnaires that assess subjective effects and reinforcement value of these products. Participants will complete a preference assessment designed to assess the relative reinforcement value of these products (see below for details). At the end of the session participants will receive an IQOS to take home with them for a one-week sampling period. Across the at-home baseline and sampling weeks, participants will complete electronic daily diaries cataloging their tobacco use.

The HTP device used will be the IQOS device. Participants will receive a rechargeable IQOS device and charger. Each Heat Stick is considered to be similar in nicotine delivery to a cigarette. Thus, to ensure participants have a full supply for the one-week period, we will provide 7 packs of Heat Sticks, one for each day. Again, this supply ensures participants could exclusively use IQOS across the entire sampling period, although we expect that the majority of participants will not do so. Heat sticks will be available in both traditional tobacco and menthol flavors (participant's choice).

Experimental Design:

Study design for both studies follows our prior and ongoing studies, and all procedures including diaries, are well established. Prior to attending the in-person screening session, participants will complete an online screening questionnaire to determine preliminary eligibility and may be consented remotely (see below for details). If consent is not completed remotely, it will be completed in person at the Screening/Baseline Session prior to collection of any data.

1) Screening/ Baseline session and Baseline Smoking Phase: Participants will attend an in-person screening session in which they complete a battery of assessments to determine eligibility. Eligible participants will then complete a series of baseline questionnaires. At the end of the baseline session, participants will be instructed to smoke as normal for a one-week baseline period. Participants will enroll in daily electronic diaries documenting their tobacco use and will complete the first diary in the lab with help of study staff. Participants will provide a urine sample for baseline assessment of cotinine (the primary metabolite of nicotine).

2) Laboratory Reinforcement Session: Participants will attend a lab session in which they sample the IQOS product and a traditional cigarette and complete questionnaires about each product they sample (see below).

Sampling and Product Questionnaires:

Participants will sample the IQOS product (n=10) and a traditional cigarette (traditional cigarette first). For each product, participants will take four puffs at their own pace, and then complete a series of questionnaires assessing the subjective effects and reinforcement value of the product (see below). There will be a 15-minute inter-product interval. When participants finish the questionnaires about each product, they will wait for the remainder of the 15 minutes to elapse before trying the next product. Participants can play on their phones or read a magazine during this time. Study staff will be able to see and hear the participant from the control room during this time and will guide the participant through the sampling session by giving directions as to when to try each product and when to start/stop questionnaires.

Preference Assessment:

At the end of the 15-minute period for the last product, participants will begin a preference assessment. For this preference assessment, participants will complete 10 trials with a 4-minute inter-trial interval. For each trial, a member of study staff will ask the participant to choose between the IQOS and a traditional cigarette. Participants will indicate which product they choose and then be allowed to take two puffs of the product at their own pace. For each trial, participants may also choose not to take any puffs.

3) At-home sampling period and Follow-up Session: Participants will be provided with an IQOS product to take home with them for a one-week sampling period. Participants will receive the IQOS product and a supply of Heat Sticks. Participants will be instructed to use their assigned product as much as they would like over the week. Participants will continue to complete the daily electronic diaries during this time period and will report use of their assigned product. The primary purpose of the daily diaries is to capture daily tobacco use more effectively than retrospective recall of tobacco use at a lab session. Participants will return to the lab following the sampling period for a follow-up session to complete additional assessments and collect expired carbon monoxide. A urine sample will be collected for cotinine analysis at this follow-up session.

Compensation: Participants will receive \$25 for the screening visit, \$75 for the lab reinforcement session, and \$50 for the follow-up session (\$150 total). Participants can earn up to \$25 per week for the daily diaries (\$50 total). Participants who complete all sessions and all diaries can earn up to \$200. Participants who are not eligible at the screening visit will receive \$15 for their time. Participants who are not eligible do not receive the full \$25 payment for that visit because the visit will be shorter (no additional baseline measures).

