Lab Session 2: Sampling: Participants will sample a traditional cigarette and the IQOS product. Participants will sample each product (four puffs at their own pace), and then wait 15 minutes before sampling the next product or beginning the preference assessment (i.e., 15-minute interproduct interval). During the interproduct interval, participants will complete questionnaires about the product they just sampled, each designed to assess the subjective effects and reinforcement value of the product they just sampled. After sampling the traditional cigarette, participants will complete three questionnaires. 1) The Cigarette Evaluation Scale, which assesses the sensory characteristics of the cigarette. Five subscales can be created from this assessment as previously described [6]: Satisfaction subscale, Psychological Reward subscale, Aversion subscale, Enjoyment of the Sensations in the Respiratory Tract subscale, and Craving subscale. 2) the Cigarette Purchase Task which assesses how many cigarettes participants estimate they would smoke at a variety of prices. As previously described [7], the following parameters can be calculated from this questionnaire: Intensity, or the number of cigarettes participants estimate they would smoke if cigarettes were free; Omax, or the maximum amount of money participants report they would spend in a single day; Pmax, or the price that produces Omax, Breakpoint, or the highest price at which participants report they would continue to smoke, and alpha, or the elasticity of demand for smoking. 3) the Perceived Health Risks scale, which assesses personal health risks associated with smoking. After sampling the IQOS product participants will complete four questionnaires.: 1) the Product Evaluation Scale, adapted from the Cigarette Evaluation Scale, which asks participants to rate the product on sensory characteristics (e.g., tasted good, immediately reduced craving for cigarettes). This questionnaire is analyzed in the same way as the Cigarette Evaluation Scale. 2) a modified Cigarette Purchase Task, in which participants estimate how many cigarettes they would smoke at a variety of prices if IQOS were also available (a test of whether the product reduces the reinforcement value of cigarettes), 3) a Product Purchase Task in which participants estimate how many Heat Sticks they would use across a series of prices if it were the only tobacco product available (a test of the reinforcement value of IQOS. Both the modified Cigarette Purchase Task and the Product Purchase Task are analyzed in the same way as the Cigarette Purchase Task. 4) a Perceived Health Risks scale, which assesses personal health risks associated with IQOS, and is the same scale used for traditional cigarettes.

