9 STATISTICAL CONSIDERATIONS AND DETERMINATION OF SAMPLE SIZE

9.1 DETERMINATION OF SAMPLE SIZE

The primary purpose of the proposal is to collect pilot data to lead to a larger grant submission. No formal power analysis has been conducted, and the sample size was chosen based on feasibility. A prior ITC pilot study conducted by [name] recruited 30 participants using a similar design with more restrictive inclusion criteria, and we anticipate being able to recruit 10 participants in the time proposed.

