9.2 DATA ANALYSIS

For each of the questionnaires completed during Visit 2 sampling, the IQOS device will be compared to traditional cigarettes using paired-sample t-tests. A chi-square test will determine whether there are differences in the percentage of participants who preferred the IQOS and the percentage who preferred traditional cigarettes during the preference assessment. For the at-home sampling phase, a within-subjects t-test will determine whether there are differences in the average number of cigarettes smoked during baseline and the sampling week.

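### At Session 2 every participant rates the cigarette first and IQOS second, so the paired t-tests on the product questionnaires cannot separate product from order

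*Combined protocol and SAP*

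**What the plan says.** The first objective (section 2.1) is "To directly compare a novel tobacco product (IQOS) vs. combustible cigarettes on subjective effects and reinforcement value".

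Section 5 (Sampling and Product Questionnaires) sets the order for everyone: "Participants will sample the IQOS product (n=10) and a traditional cigarette (traditional cigarette first". Four puffs of each product are followed by that product's questionnaires, and "There will be a 15-minute inter-product interval". Section 8 describes the same sequence: three questionnaires after the cigarette, then four after IQOS.

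Section 9.2 states that, for each Visit 2 questionnaire, "the IQOS device will be compared to traditional cigarettes using paired-sample t-tests". It has no order or period term.

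No section randomises or counterbalances the order, gives a reason for fixing it, or lists it as a limitation. At Session 3 the product questionnaires are repeated only for the take-home product, IQOS, so no cigarette rating is ever taken in second position.

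**The concern.** A within-person comparison in which all participants share one sequence carries any position effect straight into the product difference. By the time IQOS is rated, the participant has taken four cigarette puffs and completed one round of questionnaires. Craving and satisfaction ratings could plausibly shift for that reason alone. Purchase-task answers might shift too, and perceived health risks less so.

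A difference in favour of either product, or no difference, could therefore partly or wholly reflect order. Section 9.1 says "The primary purpose of the proposal is to collect pilot data to lead to a larger grant submission", so the estimate carried forward to the next study could be wrong in size or sign.

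The concern is limited to the Session 2 questionnaire comparisons. Diary cigarettes per day is a separate before/after contrast and is unaffected. In the preference assessment staff "ask the participant to choose between the IQOS and a traditional cigarette" on every trial, so the fixed order can act there only indirectly, through recency or carry-over.

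**Working it through.** The plan states no power, effect size, SD or significance level for these tests, so it has no figure to reproduce.

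**Inputs from the documents.** n = 10; cigarette first for all; paired t-test without an order term; no directional hypothesis (section 2.1).

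**Assumptions.** Two-sided 5% level; all 10 complete; effects expressed in SD of the paired difference; order effects of 0.25, 0.5 and 1.0 SD as an illustrative range.

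**Step 1: what the difference estimates.** Let D = IQOS score minus cigarette score, τ the product effect, and π the shift from being rated second rather than first.

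- Cigarette first: E(D) = τ + π
- IQOS first: E(D) = τ − π

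Under the plan only the first line occurs. There is one equation for two unknowns, so only τ + π can be estimated. This needs no assumption about size, and a larger sample in the same order would not help.

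**Step 2: error rate under the fixed order.** With τ = 0, the t statistic has 9 df and noncentrality π√10.

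| π (SD) | Noncentrality | P(significant) |
|---|---|---|
| 0 | 0 | 5.0% |
| 0.25 | 0.79 | 10.9% |
| 0.5 | 1.58 | 29.3% |
| 1.0 | 3.16 | 80.3% |

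Order can also hide a difference. With τ = 1.0 and π = −0.5, the net shift is 0.5 SD and power falls from 80.3% to 29.3%.

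**Step 3: balanced 5:5 with a period term.** The estimate is the average of the two sequence means: [(τ + π) + (τ − π)]/2 = τ. Its variance uses the pooled within-sequence variance on 5 + 5 − 2 = 8 df. In simulation with τ = 0 the rejection rate stays at about 5% for each of the three order effects.

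The loss of precision is small:

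- Effect detectable at 80% power: 1.01 SD (8 df) against 1.00 SD (9 df).
- 95% CI half-width: 2.306/√10 = 0.73 SD against 2.262/√10 = 0.72 SD.

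**Step 4: why the period term is needed.** If order is balanced but the plain paired t-test is kept, the order effect inflates the variance. The expected sample variance is 1 + 10π²/9, that is 1.28 for π = 0.5 and 2.11 for π = 1.0. Simulated power for a 1 SD product effect is then 72% and 48%, against about 79% with the period term.

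**Step 5: what balancing does not cure.** Suppose the carry-over c runs only from cigarette to IQOS. Then E(D) is τ + c in one sequence and τ in the other, and the average is τ + c/2.

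| c (SD) | Remaining bias (SD) | P(significant) when τ = 0, 8 df |
|---|---|---|
| 0.25 | 0.125 | 6.4% |
| 0.5 | 0.25 | 10.8% |
| 1.0 | 0.5 | 28.6% |

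Under the fixed order the same carry-over would act in full, giving the rates in Step 2. Unequal carry-over is credible here because all participants smoke daily, while section 4.2 excludes "any heated tobacco product use in the past 30 days".

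**The case against.** The strongest reply has four parts.

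**The consequence is limited.** The protocol attaches the words primary outcome only to diary cigarettes per day and to the preferred product. The first is unaffected and the second only indirectly affected. This is a feasibility-sized pilot, and at n = 10 an order effect of 0.25 or 0.5 SD is smaller than the CI half-width of 0.72 SD. That is true and bears on how serious the point is. It does not answer it: a small sample excuses imprecision, whereas this is an avoidable bias in a stated objective.

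**The sizes are hypothetical.** They are, and 1.0 SD has no support in the documents. Greater order-sensitivity of the purchase tasks is also a judgement. The loss of identifiability in Step 1 depends on neither.

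**Cigarette-first may be deliberate.** Section 8 describes the modified purchase task as "a test of whether the product reduces the reinforcement value of cigarettes". A cigarette-only reference taken before any IQOS exposure suits that purpose, and the fixed order provides it for all 10. This is a fair inference and a real cost of balancing. However, the protocol does not give it as a reason; section 5 says only that procedures follow earlier studies.

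**Partial safeguards exist.** The 15-minute interval may lessen carry-over, and Session 3 gives a second IQOS reading away from the cigarette. Neither makes order estimable: the interval does not change the single sequence, and Session 3 follows a week of use with no repeat of the cigarette ratings. It is also fair that section 4.2 permits occasional heated-product use more than 30 days earlier, so IQOS may not be wholly new to everyone.

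**Conclusion.** The concern holds. Product and order are completely confounded in every Session 2 questionnaire comparison, and nothing else in the documents repairs this. That conclusion rests on the design alone.

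The size is conditional on an unknown order effect. Over an assumed 0.25 to 1.0 SD, with a two-sided 5% test and 10 completers, the false-positive rate would be 10.9% to 80.3%. The direction is also unknown, so a real difference could equally be masked. The point should be fixed: the comparison is a stated objective meant to inform a larger study, and the remedy is cheap.

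**What to change.** **Preferred.**

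- In section 5, randomise the sampling order 5:5 (cigarette first or IQOS first), keeping each questionnaire with the product just sampled.
- In section 9.2, estimate each contrast as the average of the two sequence-specific mean paired differences, using the pooled within-sequence variance on 8 df.
- State as a limitation that this removes a common order effect but only reduces bias from unequal carry-over across the 15-minute interval.
- Report the modified versus cigarette-only purchase-task comparison by sequence as well as pooled.
- List the preference results by sequence too, since the product sampled just before that task would now vary.

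**Cost.** A 10-line randomisation list, a protocol amendment and one degree of freedom. The substantive downside is that participants who sample IQOS first give their cigarette ratings and cigarette-only purchase task after IQOS exposure. Only five would have a reference taken before IQOS, and a by-sequence 95% CI has half-width 2.776/√5 = 1.24 SD, against 0.72 SD with all 10.

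**Minimum, if the fixed order is kept.** Give the reason for it, and state in section 9.2 that Session 2 questionnaire differences combine product and order and will not be interpreted as product effects alone. Once the Session 2 data have been collected, only this option remains.
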